9.5.3.4 Backup of Databases

All study databases will be backed up to secure servers on a daily basis. Each data file will also be copied to an external hard drive on a weekly basis and stored off-campus. External hard drive copies of the data base will capture all versions of the data base for the previous 4 weeks.

9.6 Statistical Analysis of Study Data

9.6.1 Preliminary Analyses

Standard procedures, including frequency distributions and histograms, summary statistics (means, medians, variances, ranges), and EDA procedures (box plots, stem and leaf displays), will be used to describe the distributions of data, determine normalizing transformations (if necessary), and identify data outliers. These analyses will be conducted for all study outcome measures as well as study covariates. If continuous outcome variables are not normally distributed, normalizing transformations will be considered so that parametric analytic methods may be used; non-parametric methods may be used as an alternative.

9.6.2 Baseline Comparability

All participants will be compared between treatment arms with respect to demographic (e.g., age, race, gender), cardiac and other medical history factors, cardiovascular risk factors (including blood pressure, smoking status), dietary factors, baseline CIMT, vascular stiffness, cognition, plasma insulin, lipids/CRP, hemoglobin A1c, coagulation factors, rheology parameters and inflammatory variables. Analytical methods will include two-sample t-tests (or a non-parametric analog) for continuous variables and chi-square procedures for categorical variables. The significance level for all analyses will be set at a two-sided $\alpha=0.05$.

If multiple baseline laboratory measures are completed (e.g., at SV and at v00), the baseline value will be computed as the average of the screening measure and the v00 visit determined prior to intervention. All treatment group comparisons on baseline variables will be performed for the entire randomized study sample, for the group of participants with repeat ultrasounds, and for the group of participants without repeat ultrasounds.

9.6.3 Comparison of On-trial Changes in Laboratory and Lifestyle Variables

Treatment groups will be compared with respect to on-trial levels and on-trial changes in plasma insulin, lipids/CRP, hemoglobin A1c, coagulation factors, rheology parameters and inflammatory variables. Study groups will also be compared for on-trial levels and on-trial changes of other factors that might confound the analysis of primary end point differences. These will include analysis of dietary factors (e.g., total calories, and total calorie-adjusted calories from total, saturated, polyunsaturated, and monounsaturated fats, calories from protein, calories from carbohydrates, and dietary genistein, daidzein, and glycitein), physical activity, cardiovascular risk factors (including blood pressure, smoking status), and use of relevant nonstudy medications (including antihypertensive and lipid-lowering medications). For descriptive purposes, on-trial laboratory, dietary, clinical, and physical activity variables will be computed as the average of all on-trial determinations, weighted by the length of time between determinations. On-trial smoking will be compared as percentage of smokers versus percentage abstainers; average on-trial smoking levels (cigarettes per day) will also be computed for smokers as the average of all on-trial determinations as above. For all laboratory and clinical measures, a change variable will be computed at each on-trial measurement time as: on-trial value minus baseline value. Changes in laboratory and clinical variables from baseline will be compared within each treatment arm using generalized estimating equations to account for the repeated measurements over the study period; the model-specified correlation structure of the repeated measures will be determined by examination of the observed correlation structure. The test that the model intercept differs from 0 will comprise the overall test for significant change from baseline; incorporation of covariates for time periods of the study will test for differential change from baseline over the study period. Comparison of on-trial levels and changes in laboratory and clinical variables across treatment groups will also use generalized estimating equations, with an added covariate for randomized treatment group; interaction terms of treatment group-by-study time period will test whether treatment group differences vary over the study period. Compliance with the study product will be compared across treatment groups, also using generalized estimating equations as described. All analyses will be performed for the entire study sample and for the group of participants whose overall study product compliance is $>80\%$. The significance level for all analyses will be set at a two-sided $\alpha=0.05$.

9.6.4 Evaluation of Potential Biases and Study Validity Introduced by Differential Dropout

Possible biases introduced by differential study dropout will be evaluated by comparing:

- 1) Baseline variables (Section 9.6.2) in participants with and without repeat ultrasounds, and in participants with and without repeat cognitive testing. Analyses will be performed by two-sample t-tests, Wilcoxon rank sum, or chi-square procedures as appropriate.
- 2) On-trial variables (Section 9.6.3) evaluated within treatment group in participants with and without repeat ultrasounds, and in participants with and without repeat cognitive testing. Analyses will be performed by analysis of variance (factors for repeat ultrasound/cognitive test (yes/no) and treatment group) and Mantel-Haenszel chi-square (with stratification on treatment group) procedures.
- 3) Participants without repeat ultrasounds (or cognitive testing) by treatment group on baseline and on-trial variables (Sections 9.6.2 and 9.6.3). Analyses will be performed by two-sample t-test, Wilcoxon rank sum or chi-square procedures as appropriate.

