9.2.2.3 Data Collection Schedule

- 1) Lipid data by the precipitation method will be assessed at the screening visit (SV) and v06 and every 6 months on-trial (study visits v12, v18, v24, v30, v36).
- 2) CRP will be assessed at the screening visit (SV) and v06 and every 6 months on-trial (study visits

v12, v18, v24, v30, v36).

- 3) Hemoglobin A1c will be obtained at SV, v03 and v06 and every 6 months on-trial (study visits v12, v18, v24, v30 and v36).

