9.3.3 Data Collection Schedule

Study ultrasounds will be obtained at two pre-randomization visits, SV and v00 and every six months on-trial (study visits v06, v12, v18, v24, v30 and v36).

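### Item 2 of the dropout check (Section 9.6.4) compares on-trial values over unequal follow-up windows with no term for time, so for a variable that drifts it can signal selective dropout where none exists

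*Combined protocol and SAP*

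**What the plan says.** Section 9.6.4 lists three comparisons meant to reveal bias from dropout. Item 1 compares baseline variables between participants with and without repeat testing. Item 3 compares the treatment arms among participants without repeat testing. Item 2, the subject here, covers "On-trial variables (Section 9.6.3) evaluated within treatment group in participants with and without repeat ultrasounds", and likewise for repeat cognitive testing. Its methods are stated: "Analyses will be performed by analysis of variance (factors for repeat ultrasound/cognitive test (yes/no) and treatment group", with Mantel-Haenszel stratified on treatment group for categorical variables. Item 2 contains no term for visit, time since randomization or length of follow-up.

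For the variables themselves, item 2 points to Section 9.6.3. There, as a descriptive summary, "on-trial laboratory, dietary, clinical, and physical activity variables will be computed as the average of all on-trial determinations, weighted by the length of time" between them. No common window is set. Section 9.6.3 does handle time in its own GEE models, where "incorporation of covariates for time periods of the study will test for differential change from baseline over the study period", but Section 9.6.4 does not carry those models over.

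The schedules fix the windows:

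- Repeat scans are due "every six months on-trial (study visits v06, v12, v18, v24, v30 and v36" (Section 9.3.3).
- Cognition is tested at v00, v18 and v36 (Section 9.4.3).
- For lipids, "Lipid data by the precipitation method will be assessed at the screening visit (SV) and v06 and every 6 months on-trial" (Section 9.2.2.3). CRP follows the same visits.

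**The concern.** Having a repeat scan is close to a marker for length of follow-up. Someone who drops out before v06 has only early values. Someone with a repeat scan has values up to anywhere between month 6 and month 36. If each person is reduced to one average over whatever was observed, the two groups are averaged over different parts of the trial. Ageing, newly started antihypertensive or lipid-lowering drugs, or falling compliance can each separate the groups with no selection at all. Categorical variables such as medication use have the same problem, because a longer window gives more time to record a start.

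At stake is how the dropout check is read. A false signal would cast unwarranted doubt on the completeness of the CIMT, stiffness and cognition data. In principle a trend running against real selection could also mask it, although that direction has not been quantified.

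**Working it through.** The plan gives no dropout rate, SD, within-person correlation or time trend for this comparison, so there is no stated figure to reproduce. The only benchmark is the two-sided 5% level given in Sections 9.6.2 and 9.6.3.

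**Inputs from the documents.** N = 240 and 36 months of treatment (Section 1.3). Blood pressure is taken at months 1 to 6 and then every 3 months. The first repeat scan is at v06.

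**Assumed inputs.** Equal allocation; 5%, 10% or 15% without a repeat scan (12, 24 or 36 people); leaving times uniform over 0 to 6 months and unrelated to any variable; total variance 1; within-person correlation (ICC) 0.6, varied to 0.3 and 0.8; linear trend of 0 to 0.3 SD per year, equal in both arms.

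**Step 1: the gap created by time alone.** Weight each reading by the interval since the previous one.

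- Completer, mean reading time: [(1+2+…+6) + 3 × (9+12+…+36)] / 36 = (21 + 675) / 36 = 19.33 months.
- Leaver with last visit at month k = 1,…,5: mean reading time (k+1)/2, which averages 2 months.
- Gap: 19.33 − 2 = 17.33 months = 1.44 years. The spurious difference is therefore about 1.44 times the yearly trend, or 0.29 SD at 0.2 SD per year.

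**Step 2: hand calculation of rejection with 24 leavers.** One sixth leave before month 1 and have no reading, so 20 leavers are compared with 216 stayers.

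- Variance of a completer's average: 0.6 + 0.4 × (6×1 + 10×9)/36² = 0.6 + 0.4 × 0.074 = 0.630.
- Variance of a leaver's average: 0.6 + 0.4 × (1 + 1/2 + 1/3 + 1/4 + 1/5)/5 = 0.6 + 0.4 × 0.457 = 0.783.
- True standard error: √(0.783/20 + 0.630/216) = 0.205. ANOVA pools the variance and uses about 0.187.
- Effective cut-off: 1.97 × 0.187/0.205 = 1.80 true standard errors, so the test is too liberal even with no trend.
- At 0.2 SD per year: shift 0.289/0.205 = 1.41; P(Z > 1.80 − 1.41) is about 35%.

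**Step 3: simulation of the planned ANOVA under completely random dropout** (1,500 to 2,000 runs per setting), beside the hand calculation:

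| Trend (SD/year) | Levels, by hand, 10% leavers | Levels, simulated, 10% leavers | Levels, simulated, 5% / 15% leavers | Change from baseline, simulated, 10% leavers |
|---|---|---|---|---|
| 0 | 7.2% | 6.5% | 8.4% / 7.8% | 8.8% |
| 0.1 | 14.3% | 13.6% | 10.8% / 17.7% | 18.9% |
| 0.2 | 34.9% | 34.9% | 21.0% / 46.9% | 45.7% |
| 0.3 | 62.3% | 61.7% | 39.5% / 74.3% | 75.4% |

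**Step 4: sensitivity, 10% leavers.**

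- ICC 0.3, trend 0 to 0.3: 11.5% to 78.6% on levels. ICC 0.8: 5.8% to 51.9%.
- If 20% of stayers leave between months 6 and 36, the 0.2 SD per year figure falls from 34.9% to 27.3% on levels (40.3% on changes).
- Insulin schedule (only v03 before v06), trend 0 and 0.2: 9.3% and 27.3% on levels. Coagulation schedule (week 1 and v01 before v06): 6.9% and 39.7%.

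**Step 5: confirming the cause.** With everyone compared at one common visit (v01), the same ANOVA rejects 4.6%. With stayers cut to leaving times drawn from the leavers' distribution, rejection is 4.4% to 5.5% on levels and 3.1% to 5.2% on changes across all four trends.

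**Step 6: lipids and CRP.** The first scheduled on-trial value is at v06, the visit of the first repeat scan. A participant who leaves before v06 has no scheduled value, whatever the test.

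The cognition split was not simulated. There the windows are up to about 18 months against 18 to 36.

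**The case against.** The best objection is that Section 9.6.4 never says it uses the averages. Section 9.6.3 offers them as descriptive, and it also defines a change from baseline at each measurement time, which could be analysed visit by visit with no window problem. This is right as far as it goes: use of the average is an inference. It is a strong one. A two-factor ANOVA needs one value per person, the average is the only general per-person on-trial summary that Section 9.6.3 defines, and item 2 has no visit factor. If something else was meant, the text has to say so.

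A reader might go further and infer that the test will reject because of time on trial. The documents do not support that. Rejection well above 5% needs a drifting variable, and even at 0.2 SD per year most simulated trials did not reject with 10% leavers. A reader might also infer a contrast of under 6 months against 3 years. Three years applies only to completers, since one follow-up scan is enough to count as having a repeat (Section 9.6.5.1). Six months applies only to the ultrasound split, give or take the visit window. A few people may attend later visits without a usable scan; Section 8.4 puts unreadable cases below 1%.

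It is also fair that this is one check of three. Item 1 uses baseline values. Item 3 compares arms among people without repeat testing, so it has no leaver-versus-stayer mismatch. A drift common to both arms loads on the repeat yes/no factor and creates no difference between arms by itself. Section 9.6.4 states no formal null and attaches no decision rule, and the primary mixed model does not use the result.

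**Conclusion.** The point holds as a flaw in item 2 alone. Under the natural reading, its stated method compares unequal follow-up windows without adjusting for time, and can report selective dropout that is only elapsed time. On levels with ICC 0.6, a nominal 5% test rejects about 6% to 8% with no trend (5% to 15% leavers). With 10% leavers it rejects about 14%, 35% and 62% at 0.1, 0.2 and 0.3 SD per year, and somewhat less if stayers also leave early. These sizes rest on assumed dropout, trend and correlation, and on the inference that whole-trial averages are used. The absence of lipid and CRP values in those who leave before v06 rests on the schedule alone. The efficacy analyses are untouched, so this is a minor correction worth making before the dropout analyses are run.

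**What to change.** In Section 9.6.4 item 2:

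- Replace the two-factor ANOVA on whole-trial averages with a repeated-measures model (GEE or mixed) on visit-level values. Restrict it to visits before v06 for the ultrasound split and before v18 for the cognition split, with visit, repeat test yes/no and treatment as factors.
- Compare categorical variables such as medication use over the same restricted visits.
- State that variables with no scheduled determination in the window, such as lipids and CRP before v06, are covered only by the baseline comparison in item 1.

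The matched-window version was simulated and returned to about 5%. The visit-level model was not simulated, but it removes the same mismatch and follows the approach that Section 9.6.3 already uses. The cost is a few sentences of SAP text and a restricted-window data step, with no new data. Stayers' later values go unused in this one check.

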9.6.5 Analysis of Study Outcomes

All analyses of study outcomes will be conducted on an intent-to-treat basis. All participants with baseline and any follow-up end point data, regardless of their dropout and compliance status, will be analyzed according to their randomized treatment group. Statistical assumptions of the planned analyses will be verified. Alternative analyses will be performed if the assumptions of the planned analyses are not justified. Key assumptions that will be verified are: 1) normality of primary end point; 2) homogeneity of variances between treatment groups; and, 3) deviations from linearity in the regression of end point measurements (CIMT, arterial stiffness, cognition) against time on-study.

9.6.5.1 Primary Efficacy Analysis: Carotid Artery IMT Analyses

The primary end point will be the per-subject rate of change in the right distal CCA far wall IMT. The rate of change in the right distal CCA far wall CIMT will be computed for each participant by fitting a regression line of CIMT on years since baseline ultrasound. The estimated slope of the regression line will be used as that subject's CIMT rate of change. Analyses of trial end points will be performed on the intent-to-treat sample, which will be defined as all randomized participants who had a baseline and at least 1 follow-up CIMT measurement taken after randomization.

The statistical approach outlined above will be accomplished using mixed effects models for longitudinal data, with the randomization stratification variable (dichotomized baseline CIMT) used as a covariate. Each CIMT measure will be included as a dependent variable. The regression coefficient associated with the model covariate of time on-study will estimate the average group progression rate of CIMT (in mm/year). Random effects terms for the regression intercept and slope (change over time) will allow for individual participant deviations from their group average in baseline CIMT and CIMT rate of change, respectively. The statistical test for differences in the CIMT rate by treatment group will be accomplished by adding a treatment group by time on-study interaction term. The significance of the regression coefficient associated with this interaction term is the test that the CIMT rates differ by treatment group. We will also evaluate baseline plasma levels of insulin, lipids/CRP, hemoglobin A1c, coagulation factors, rheology parameters and inflammatory variables, dietary nutrients, smoking, blood pressure, physical activity and use of non-study medications as potential confounders. If any of these variables are found to be confounders of treatment-rate of CIMT relationship, they will be included as

covariates in the analysis.

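### The set called intent-to-treat leaves out randomized participants with no follow-up CIMT, although the planned mixed model could include them; if early loss differs by arm, this can modestly bias the slope contrast

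*Combined protocol and SAP*

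**What the plan says.** Section 9.6.5 states: "All analyses of study outcomes will be conducted on an intent-to-treat basis". It then limits the analysis to people with follow-up: "All participants with baseline and any follow-up end point data, regardless of their dropout and compliance status, will be analyzed" according to their randomized group. Section 9.6.5.1 repeats the limit for CIMT, defining the intent-to-treat sample as "all randomized participants who had a baseline and at least 1 follow-up CIMT measurement taken after randomization".

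Section 9.6.5.1 describes the primary end point in two ways. The first is a per-person regression: "The estimated slope of the regression line will be used as that subject's CIMT rate of change". The second, by which the analysis is to be carried out, is a mixed model:

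- Outcome: "Each CIMT measure will be included as a dependent variable".
- Random effects: "Random effects terms for the regression intercept and slope (change over time) will allow for individual participant deviations" from the group average.
- Stratum: the model is fitted "with the randomization stratification variable (dichotomized baseline CIMT) used as a covariate". No stratum-by-time term is stated.
- Test: "The statistical test for differences in the CIMT rate by treatment group will be accomplished by adding a treatment group by time on-study interaction term".

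Section 9.3.3 schedules scans at SV and v00, before randomization, and then every six months from v06 to v36. Section 9.6.5.2 carries the CIMT methods over to arterial stiffness.

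**The concern.** Whether a participant has a follow-up scan is known only after randomization. Anyone lost before the month 6 scan leaves the primary analysis, so the groups compared are those retained, not those randomized. The name intent-to-treat suggests otherwise.

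The exclusion is also unnecessary under the stated model. A participant with only the SV and v00 scans has two observed values of the dependent variable and can enter the likelihood. Such a record adds almost nothing to the precision of the slope. It does help the likelihood analysis remain valid when early loss depends on observed baseline CIMT. If such loss differs between arms, the retained arms differ in baseline thickness. If progression is also associated with thickness, they then differ in average slope without any treatment effect. The co-primary CIMT contrast is at stake, and by section 9.6.5.2 the stiffness contrasts follow the same rule.

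**Working it through.** **No plan figure to reproduce.** The documents give N = 240 without an effect size, variance, power or dropout rate, so the size of the problem can only be shown under assumptions.

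**Inputs from the documents.** N = 240 (1.3). Two baseline scans and six follow-up scans (9.3.3). Stratum cut 0.75 mm (4.2). Measurement CV below 3% (8.3.2), hence error SD of at most 0.03 × 0.75 = 0.0225 mm at the cut; 0.0225 mm is used.

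**Assumed inputs.** 1:1 allocation (120 per arm), mean CIMT 0.77 mm, between-person SD 0.11 mm, mean slope 0.006 mm/yr with SD 0.010, and intercept-slope correlation 0, +0.3, -0.3 or +0.6. No true treatment effect.

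**Model.** CIMT = arm + time + arm × time + stratum + random intercept + random slope + error, fitted by maximum likelihood. Early loss follows logit P(no follow-up scan) = c + g·z, where z is standardized observed baseline CIMT and g = ln 3 ≈ 1.1 (odds ratio 3 per SD). Bias comes from 400,000 simulated participants per arm, and the SE is rescaled to 120 per arm. The SE of the contrast is about 0.0017 mm/yr whether or not the baseline-only participants are kept.

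**Loss that works alike in both arms.** Random loss of 10%, or 10% loss in each arm with odds ratio 3 toward high CIMT: contrast bias about 0 at every correlation. Both arm slopes can shift together (for example from 0.0060 to 0.0055 at correlation 0.6), and the shift cancels.

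**Loss that differs by arm.** Absolute bias in mm/yr:

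| Loss before any follow-up scan | Correlation | Plan's set | All randomized, stratum main effect only | Share removed |
|---|---|---|---|---|
| 10% per arm, opposite directions | -0.3 | 0.00070 | 0.00039 | 44% |
| 10% per arm, opposite directions | +0.6 | 0.00107 | 0.00059 | 45% |
| 10% in one arm only | -0.3 | 0.00034 | 0.00017 | 50% |
| 10% in one arm only | +0.6 | 0.00054 | 0.00027 | 50% |
| 5% v 15%, both toward high CIMT | -0.3 | 0.00040 | 0.00027 | about 33% |
| 5% v 15%, both toward high CIMT | +0.6 | 0.00051 | 0.00028 | 45% |
| 5% per arm, opposite directions | -0.3 | 0.00039 | 0.00022 | 44% |

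Share removed = 1 - (all randomized / plan's set), for example 1 - 0.00039/0.00070 = 44%. Across the settings examined it is about 30-55%.

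**Against the SE.** 0.00070/0.0017 = 0.41 and 0.00107/0.00169 = 0.63. With d = bias/SE and a two-sided 5% test, type I error = 1 - [Φ(1.96 - d) - Φ(-1.96 - d)], giving 7.0% and 9.7%. At correlation 0, opposite 10% loss leaves about 0.0001 mm/yr, which arises through measurement error. The lower end of the range, 0.03 SE, is 0.03 × 0.0017 = 0.00005 mm/yr, which rounds to 0.0001. With loss of 5% or less and odds ratios of 2 to 3, bias is 0.0001 to 0.0004 mm/yr and type I error 5.0-5.6%.

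**Why inclusion alone is not enough.** The stratum is itself a cut of baseline CIMT. As a main effect only, it takes the between-stratum difference out of the intercepts but gives it no path to the slopes. The early leavers' records then correct only the within-stratum part.

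**Adding stratum-by-time** (opposite 10% loss):

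| Analysis | Correlation -0.3 | Correlation +0.6 |
|---|---|---|
| All randomized, stratum and stratum-by-time | below 0.0001 | below 0.0001 |
| Plan's set, stratum and stratum-by-time | 0.0003 | 0.0005 |

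Both changes are needed in these settings, and neither raises the SE.

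**The case against.** **The excluded people have no slope.** The end point is a per-person rate of change, and two scans about two weeks apart say nothing useful about it. That is right for precision: including them leaves the SE unchanged. It does not settle bias, since the planned test comes from the mixed model, where these records inform the intercepts.

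**The plan already looks for this.** Section 9.6.4 compares baseline variables in people with and without repeat ultrasounds, and compares those without by treatment group. Section 9.6.2 repeats the baseline comparisons, including baseline CIMT, in the same subsets. Section 5.3 urges people who stop product to complete their scans. This stands as far as it goes: a reader should not infer that differential dropout was ignored. But these are diagnostics and retention measures. No analysis is stated for the case where they show an imbalance.

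**The loss pattern is hypothetical.** The documents give no reason why loss should depend on CIMT differently by arm in a double-blind trial of healthy people. This stands, and it is why the point is minor.

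**Stronger readings that the documents do not support:**

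- A reader might infer that any early loss related to baseline CIMT biases the contrast. With the same mechanism and rate in both arms and a constant effect, it does not.
- A reader might infer that fitting the stated model to everyone randomized removes the bias. With the stratum as a main effect only, it does not.
- A reader might take inclusion as general protection. When the treatment effect itself varied with baseline CIMT and loss was alike in both arms, the contrast shifted by 0.0005 mm/yr with or without the early leavers.

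**Conclusion.** The concern holds in a limited form. The set is a modified intent-to-treat set under the intent-to-treat name, and the planned model does not need the restriction. Bias in the treatment-by-time contrast requires early loss related to baseline CIMT that differs by arm, together with an association between progression and baseline CIMT. Under the assumed variances with 5-15% early loss, it is about 0.0001 to 0.0011 mm/yr, roughly 0.03 to 0.6 SE. It is negligible if loss is small or unrelated to baseline CIMT.

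Larger values, 0.0012 to 0.0028 mm/yr (0.7 to 1.7 SE), appeared only under an extreme stress test: near-deterministic 15% loss in opposite directions with a non-zero correlation. They should not be read as the expected size. All magnitudes rest on assumed inputs apart from N, the scan schedule, the stratum cut and the CV bound. No magnitude was computed for stiffness. Severity: minor.

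**What to change.** 1. In 9.6.5 and 9.6.5.1, define the intent-to-treat set for CIMT as all randomized participants, analysed as randomized, with every available CIMT (SV, v00 and on-trial) in the mixed model.
2. In 9.6.5.1, enter the stratification variable both as a main effect and by time.
3. In 9.6.5.2, apply the same set and model to the stiffness end points. Cognition (9.6.5.3) is modelled as change from baseline, so baseline-only records cannot enter there and this change does not apply.
4. Keep the present set as a sensitivity analysis under the name participants with at least one follow-up scan, and report the number without a follow-up scan and their baseline CIMT by arm.

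The cost is SAP wording plus reading the v00 scans of early leavers. Section 9.3.1 has SV scans read at once and the rest in batches as participants complete the trial, so the wording should make sure that these scans are included. Including these participants brings no loss of precision and no gain in it. The change should be made before unblinding.
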